8.2.3.4 Health Economics Analysis

The health economics analysis will be done by a separate vendor and is not a part of this SAP; however, data relating to health resource utilization, feeding into the health economics analysis, will be summarized using the PFS-FAS as described in this section. All data relating to health resource utilization will be listed.

Health resource utilization data will be used to support health economic evaluations. Study specific analyses will focus on descriptive statistics of the variables described below occurring during the randomized treatment period and will be summarized by treatment arm as described in Section 5 for categorical and continuous variables. Survival analyses of time to disease-related pain and time to first use of opioid analgesics will be conducted similarly as described in Section 8.2.3.3.1 for EQ-5D-5L utility score.

1. Hospital admissions

- Number of hospitalizations both as a categorical variable and a continuous variable
- Hospitalizations (yes/no) (admitted as in-patient)
- LOS per hospitalization episode will be estimated and the total LOS in the hospital per patient will be summarized.
- Total Number of symptomatic skeletal events (SSEs; includes symptomatic pathological bone fracture, spinal cord compression, tumor-related orthopedic surgical intervention, or requirement for radiation therapy to

relieve bone pain; captured in 3 CRFs: Adverse Events, Concurrent Surgical/Therapeutic Procedures, and Radiotherapy)

- Number of hospitalizations for SSEs
2. Duration of time in hospital following ¹⁷⁷Lu-PSMA-617 administration (hours) is the time span of patient discharge as captured on the ¹⁷⁷Lu-PSMA-617 administration CRF.
 3. Concomitant drug category use (frequency of administration, dose (listed only); total number of days administered = end date-start date + 1). The list of concomitant drugs as captured on the concomitant medication/therapy CRF page to include in each category will be pre-specified and flagged prior to the pre-planned analyses.
 - (1) Bisphosphonates (including but not limited to zoledronic acid, alendronic acid, etc.), denosumab, and other bone targeted therapies)
 - (2) Corticosteroids for systemic use
 - (3) Antifungals for systemic use (i.e. ketoconazole)
 - (4) ESA (erythropoietin stimulating agents, i.e. epoetin alfa)
 - (5) Granulocyte macrophage colony-stimulating factor (GM-CSF)
 - (6) Novel androgen axis drugs (NAADs; i.e. enzalutamide, abiraterone, apalutamide)
 - (7) Antiemetics
 - (8) Opioid analgesics use for cancer-related pain
 1. Time to disease-related pain (TDRP or Time to worsening of Worst Pain Intensity as defined in Section 8.2.3.3.3)
 2. Time to first use of opioid analgesics (TFOA, defined below)
 4. Therapeutic interventions (frequency; total number of days administered = end/stop date – start date + 1)
 - Local external beam radiotherapy, including palliative external radiation as captured on the concurrent radiotherapy CRF page.
 - Blood transfusion (full blood or derivatives). The list of concomitant blood transfusions captured on the concomitant medication/therapy CRF page to include will be pre-specified and flagged prior to the pre-planned analyses.

Variable definitions:

Time to first use of opioid analgesic (TFOA) – TFOA is defined as days from randomization to the first occurrence of first need of pain and opioid analgesic use (OAU) as indicated in concurrent medications), clinical disease progression (excluding radiographic and PSA progression), or death. If no event is experienced, censoring date is the later of date of last visit and last concomitant medication recorded.

8.2.4 Sub-study

At the time of the final analysis of cumulative safety data of the sub-study patients (Section 4.2), limited efficacy data (excluding patient reported outcomes) will be summarized

descriptively (i.e. no hypothesis testing will be performed) for the ¹⁷⁷Lu-PSMA-617+BSC/BSoC arm using the Sub-study Safety Analysis Set.

9. Safety Evaluation

Safety analyses will be presented using the PSMA-11 Safety Analysis Set or the FAS Safety Analysis Set except for study drug exposure (specifics in Section 9.1), ⁶⁸Ga-PSMA-11 adverse events (PSMA-11 Safety Analysis Set only), randomized treatment adverse events and adverse events during long-term follow-up (FAS Safety Analysis Set only) and prior/concurrent/post-therapies (specifics in Section 9.5, 9.6 and 9.7). Safety analyses of laboratory values and vital signs using the PSMA-11 Safety Analysis Set will only include assessments done at screening.

For the PSMA-11 and FAS safety analysis sets, tables will show results by treatment arm and for all patients combined. For the PSMA-11 Safety Analysis Set, an additional column will be included for patients not enrolled (i.e. not randomized).

Listings will be created by treatment arm.

9.1 Extent of Exposure

⁶⁸GA-PSMA-11 Exposure

For the PSMA-11 Safety Analysis Set, the variables to be summarized for ⁶⁸GA-PSMA-11 exposure are:

- ⁶⁸GA-PSMA-11 activity injected-decay corrected dose (MBq)
- ⁶⁸GA-PSMA-11 activity injected-decay corrected dose per body weight (MBq/kg)

Randomized Treatment Exposure, Summary of Cycles

For the FAS Safety Analysis Set, summary of treatment cycles variables to be included are:

Randomized treatment exposure, for both treatment arms:

- Duration of exposure to randomized treatment (months) (definition in Section 5.6)
- Number of cycles started per patient (both as categorical and continuous variable)
- Average duration of randomized treatment cycles (months) (definition in Section 5.6)
- Number of patients with at least one cycle delayed
- Number of cycles delayed with reasons for delay

¹⁷⁷Lu-PSMA-617 exposure, for the Lu-PSMA-617 + BSC/BSoC arm:

- Number of patients with at least one dose interrupted (omitted) with the reasons for interruption overall and by cycle
- Number of patients with at least one dose reduced with the reasons for dose reduction overall and by cycle

Randomized Treatment Exposure, By Cycle and Across Cycles Combined

¹⁷⁷Lu-PSMA-167 exposure, for the Lu-PSMA-617 + BSC/BSoC arm

For the FAS Safety Analysis Set investigational treatment arm, ¹⁷⁷Lu-PSMA-167 exposure variables to be summarized (definitions in Section 5.6) are:

- Cumulative dose (GBq) of patient for the entire study overall
- Dose intensity per cycle (GBq/cycle) for each cycle
- Dose intensity (GBq/month) for the entire study overall
- Relative cycle dose intensity (%) for each cycle
- Relative dose intensity (%) for the entire study overall

BSC/BSoC exposure, for both treatment arms

For the FAS Safety Analysis Set (both treatment arms), variables to be tabulated for BSC/BSoC for the entire study and for each treatment cycle are:

- Concomitant medications indicated as study BSC/BSoC, coded using WHO Drug Global dictionary. The WHO Drug Global dictionary version used for reporting will be specified as a footnote in the applicable tables and listings. A pre-specified list of concomitant medications, based on the interventions allowed as BSC/BSoC per protocol (protocol section 5.2) will be used to indicate and flag concomitant medications as study BSC/BSoC. The BSC/BSoC flag captured on the CRF will not be used to identify concomitant medications indicated as study BSC/BSoC.
- Concurrent procedures other than radiotherapy indicated as study BSC/BSoC, coded using MedDRA. The MedDRA version used for reporting will be specified as a footnote in the applicable tables and listings. The BSC/BSoC flag captured on the CRF will be used to identify concurrent procedures other than radiotherapy indicated as study BSC/BSoC.
- Concurrent radiotherapy indicated as study BSC/BSoC. The BSC/BSoC flag captured on the CRF will be used to identify concurrent radiotherapy indicated as study BSC/BSoC.

Additionally, a summary of the number (%) of patients who received a NAAD as study BSC/BSoC, type of NAAD received (by WHO Drug preferred name) and duration of exposure will be provided by treatment arm and overall using the FAS Safety Set. All concomitant medications, concurrent procedures and radiotherapies flagged as study BSC/BSoC will be listed.

9.1.1 Sub-study

⁶⁸GA-PSMA-11 exposure will be summarized using the PSMA-11 Sub-study Analysis Set. Study treatment and ¹⁷⁷Lu-PSMA-617 exposure will be summarized as described above using the Sub-study Safety Analysis Set.

9.2 Adverse Events and Deaths

Adverse events (AEs) will be coded using the Medical Dictionary for Regulatory Activities (MedDRA) preferred term (PT) and system organ class (SOC) and will be graded according to the National Cancer Institute Common Terminology Criteria for AEs (NCI CTCAE criteria [v5.0]). The MedDRA version used for reporting will be specified as a footnote in the applicable tables and listings.

9.2.1 Definition of Treatment Emergent Adverse Events (TEAEs)

⁶⁸GA-PSMA-11

PSMA-617-01 SAP Version 3.0
18Jan2021

Page 53 of 79

This information is confidential or privileged information and trade secrets of Endocyte, Inc.

A ^{68}Ga -PSMA-11 TEAE is defined as an AE that was not present prior to dosing with ^{68}Ga -PSMA-11 but appeared following dosing, or was present at time of dosing but worsened during or after dosing.

The treatment-emergent period will be defined as the period from the date of ^{68}Ga -PSMA-11 dosing up to 6 days after the date of ^{68}Ga -PSMA-11 dosing as long as prior to the first dose of ^{177}Lu -PSMA-617 for the investigational arm and prior to Cycle 1 Day 1 for the BSC/BSoc arm.

AEs reported as "possibly", "probably", or "definitely" related to ^{68}Ga -PSMA-11 that occur beyond the 6-day reporting window but occur before the initiation of randomized treatment are also ^{68}Ga -PSMA-11 TEAEs. Unrelated ^{68}Ga -PSMA-11 AEs that occur beyond 6 days will not be TEAEs.

Randomized treatments

A randomized treatment TEAE is defined as an AE that was not present prior to initiation of randomized treatment, defined as first dose of ^{177}Lu -PSMA-617 for the investigational arm and Cycle 1 Day 1 for the BSC/BSoc arm, but appeared following treatment, or was present at treatment initiation but worsened during treatment. An AE that was present at treatment initiation but resolved and then reappeared while the patient was on treatment is a TEAE (regardless of the intensity of the AE when the treatment was initiated).

The treatment-emergent period will be defined as the period from the date of initiation of randomized treatment up to 30 days after the date of the last administration of randomized treatment or the day prior to the initiation of subsequent anticancer treatment, whichever occurs first.

9.2.2 General Convention

Any treatment-emergent event as defined in Section 9.2.1 missing the assessment of relatedness will be considered study drug-related.

In case a patient experienced the same event more than once, the maximum toxicity grade will be presented.

In all AE tables except the ones presented by Cycles, multiple occurrences of the same adverse events occurring in one individual are counted only once.

In all AE tables presented by cycle of onset, multiple occurrences of the same adverse events occurring in one individual within one cycle are counted only once.

AE summaries for ^{68}Ga -PSMA-11 and Randomized Treatment will include AEs occurring during the treatment-emergent period whereas AE summaries for Long-term Follow up will include new and existing AEs during the long-term follow-up period captured on the Long-Term Follow up CRF page. All AEs will be listed along with the information collected on those AEs. AEs will be summarized by number and percentage of patients having at least one AE, having at least one AE in each primary SOC and for each PT using MedDRA coding. The total number of events will also be provided. A patient with multiple occurrences of an AE will be counted only once in the respective AE category. A patient with multiple CTCAE toxicity grades for the same preferred term will be summarized under the maximum CTCAE toxicity grade recorded for the event. AE with missing CTCAE toxicity grade will be included in the total across all grades of the summary table.

In all AE summaries, the primary SOC will be presented alphabetically and the PTs will be sorted within primary SOC in descending frequency. The sort order for the PT will be based on their frequency in the ^{177}Lu -PSMA-617+BSC/BSoc arm for randomized treatment and long-term follow-up AE summaries and the frequency in the overall column for ^{68}Ga -PSMA-11 AE summaries.

9.2.3 ⁶⁸Ga-PSMA-11 Adverse Events

A summary table using the PSMA-11 Safety Analysis Set including the number of patients with at least one event, and the total number of events will be presented for the following variables:

- TEAE¹
- serious TEAE¹
- grade 3/4/5 TEAE²
- drug-related TEAE¹
- serious drug-related TEAE¹
- drug-related grade 3/4/5 TEAE²
- fatal TEAE²

¹AE variables to be tabulated by SOC and PT by grade including a total across all grades and all grades 3/4/5.

²AE variables to be tabulated by SOC and PT.

A summary of serious and non-serious adverse events with number of occurrences will be produced (an occurrence is defined as >1 day between start and prior end date of record of same preferred term).

A listing will include the participant identifier, age, race, verbatim, preferred term, duration of the event, toxicity grade, seriousness, action taken regarding ⁶⁸Ga-PSMA-11, outcome, relationship to study drug, and start and end date. Non-treatment-emergent adverse events will be flagged.

9.2.3.1 *Sub-study*

Similar analyses as described in Section 9.2.3 will be done using the PSMA-11 Sub-study Analysis Set.

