3.4.5 Duration of Subject Participation

Patients may continue treatment until radiographic progressive disease, withdrawal of consent, the occurrence of unacceptable toxicity, or a determination by the investigator the patient is not clinically benefiting. As per the patient's physician, when the participant requires care that is not allowed on study, the participant will discontinue treatment and enter the long-term follow-up period. While the patient and/or physician may decide prematurely to cease taking randomized therapy at any time, full follow-up of all randomized patients for the intended duration of the trial is planned by design for the collection of rPFS and OS data.

It is anticipated that it will take approx. 14 months to randomize the required 814 patients in the study. After the last patient is randomized patients will be followed for up to 24 months or at least until 508 deaths have occurred. The maximum duration of the study, from first date of randomization to last follow-up, will therefore be approximately 38 months.

After final analysis of the OS primary endpoint, long-term follow-up will be extended until a separate long-term safety follow-up study is available in the respective country, until patient death or until patient withdrawal of consent, whichever occurs first. The maximum duration of the study, from first date of randomization to last follow-up, will therefore be up to approximately 66 months.

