7.2 Evaluating and recording adverse events

Before final analysis of alternate primary endpoint OS:

All AEs will be graded according to CTCAE v5.0. All AE monitoring and SAE recording and reporting will begin at the time of consent and will continue up to and including 30 days after the last dose of ¹⁷⁷Lu-PSMA-617 or the date of best supportive/best standard of care end of treatment decision, whichever is later. For patients that are not randomized, AE monitoring will continue up to and including 6 days after administration of ⁶⁸Ga-PSMA-11.

All AEs and abnormal test findings, regardless of suspected causal relationship to ⁶⁸Ga-PSMA-11, ¹⁷⁷Lu-PSMA-617, and/or best supportive/best standard of care, will be recorded in the patients' case histories. For all AEs sufficient information will be obtained to permit an adequate determination of the outcome of the event and an assessment of the causal relationship between the AE and ⁶⁸Ga-PSMA-11, ¹⁷⁷Lu-PSMA-617, and/or best supportive/best standard of care. AEs or abnormal test findings felt to be associated with ⁶⁸Ga-PSMA-11, ¹⁷⁷Lu-PSMA-617, and/or best supportive/best standard of care will be followed until the event or its sequelae or the abnormal test finding resolves or stabilizes at a level acceptable to the investigator.

The investigator will promptly review AEs and abnormal test findings to determine if: 1) the abnormal test finding should be classified as an AE; 2) there is a reasonable possibility that the

AE was caused by ⁶⁸Ga-PSMA-11, ¹⁷⁷Lu-PSMA-617, and/or best supportive/best standard of care; and 3) the AE meets the criteria for a serious adverse event (SAE). If the final determination of causality is “unknown and of questionable relationship to the study drug” the adverse event will be classified as associated with the use of the study drug for reporting purposes. If the final determination of causality is “unknown but not related to the study drug” the determination and rationale will be documented in the patient’s case history.

After final analysis of alternate primary endpoint OS:

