8.8.1 Extent of exposure

The duration of exposure and dose intensity will be calculated. The relationship between dose intensity, duration of exposure, and frequency and severity of adverse events will be explored by data tabulation.

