Vital signs at baseline	the last available assessment on or before the date of start of randomized treatment or if a time assessment is captured, the 15 minutes pre-dose value on or before the date of start of randomized treatment	Safety for randomized treatment
Vital signs at screening	the last available assessment on or before the date of ⁶⁸ Ga-PSMA-11 dosing	Safety for ⁶⁸ Ga-PSMA-11
ECG at baseline	the last available assessment on or before the date of start of randomized treatment	Safety for randomized treatment
ECG at screening	the last available assessment on or before the date of ⁶⁸ Ga-PSMA-11 dosing	Safety for ⁶⁸ Ga-PSMA-11
1. For the sub-study, randomized treatment refers only to ¹⁷⁷ Lu-PSMA-617+BSC/BSoC.		

Cycle 1 Day 1 (C1D1) is date of first study procedures, randomized treatment and assessments.

Date of randomization is used for the start date of "time to" endpoints for efficacy analyses.

⁶⁸Ga-PSMA-11 dosing is the date ⁶⁸Ga-PSMA-11 was administered.

Date of last randomized treatment administration is the date of last administration of randomized treatment which is the date of last administration of ¹⁷⁷Lu-PSMA-617 or date of last administration of BSC/BSoC, whichever is later. For example: if the last dose administration of ¹⁷⁷Lu-PSMA-617 is on 15APR2019, and the end of treatment decision

date for BSC/BSoC is on 17APR2019, then the date of last administration of randomized treatment is on 17APR2019.

- Date of last administration of ¹⁷⁷Lu-PSMA-617 is the last date when ¹⁷⁷Lu-PSMA-617 was administered (non-zero dose), i.e. the latest date of administration as captured on the ¹⁷⁷Lu-PSMA-617 Administration CRF page with a non-zero dose.
- Date of last administration of BSC/BSoC is the end of treatment decision date recorded on the End of Treatment – BSC/BSoC CRF.
- Date of last administration of a NAAD as study BSC/BSoC will be defined as follows:
 - = latest end date of a NAAD indicated as study BSC/BSoC (captured on concomitant medications CRF) if before date of last administration of BSC/BSoC, otherwise
 - = date of last administration of BSC/BSoC.

For example: if the latest end date of a NAAD indicated as study BSC/BSoC is 01AUG2019 and the date of last administration of BSC/BSoC is 03OCT2019, then the date of last administration of a NAAD as study BSC/BSoC is 01AUG2019.

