9.2.4 Randomized Treatment Adverse Events

A summary table using the FAS Safety Analysis Set including the number of patients with at least one event, and the total number of events will be presented for the AE variables below.

- TEAE^{1, 3}
- Serious TEAE^{1, 3}
- Grade 3/4/5 TEAE²
- Drug-related TEAE¹
- Serious drug-related TEAE¹
- Drug-related grade 3/4/5 TEAE²
- TEAE leading to reduction of ¹⁷⁷Lu-PSMA-617 dose¹ or of BSC/BSoc¹
- TEAE leading to interruption of ¹⁷⁷Lu-PSMA-617 treatment¹ or of BSC/BSoc¹
- TEAE leading to permanent discontinuation of ¹⁷⁷Lu-PSMA-617 treatment¹ or of BSC/BSoc¹
- Fatal TEAE²

¹AE variables to be tabulated by SOC and PT by grade (including a total across all grades and all grades 3/4/5).

²AE variables to be tabulated by SOC and PT.

³TEAEs are to be tabulated by SOC and PT, including a total across all grades and all grades 3/4/5), and by ¹⁷⁷Lu-PSMA-167 cycle of onset.

A summary of serious and non-serious adverse events with number of occurrences will be produced (an occurrence is defined as >1 day between start and prior end date of record of same preferred term).

A listing for each patient will include the same variables as mentioned above in Section 9.2.3 except will include action taken regarding ¹⁷⁷Lu-PSMA-617 and action taken regarding Best supportive/Best standard of care. Non-treatment-emergent adverse events will be flagged.

To help evaluate the impact of the COVID-19 virus on the safety, the incidence of COVID-19 related adverse event preferred terms will be presented incorporating (a) COVID-19 related adverse events with an onset date prior to the start of the outbreak (i.e. pre-2020) and (b) all COVID-19 related adverse events occurring before the data cut-off. All COVID-related AEs will be included in the listings.

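### Randomized-treatment AEs are compared between arms only as crude percentages and event counts, over a window that ends at each patient's own end of treatment and is probably longer on 177Lu-PSMA-617

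*SAP*

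**What the plan says.** SAP 9.2.2 sets the general rule: "AEs will be summarized by number and percentage of patients having at least one AE". It adds: "The total number of events will also be provided". SAP 9.2.4 applies this to randomized treatment in the FAS Safety Analysis Set, with a summary table "including the number of patients with at least one event, and the total number of events" for any, serious, grade 3/4/5, drug-related and fatal TEAEs, among others. SAP section 9 has these tables shown by arm. Neither the percentages nor the counts are divided by patient-time.

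SAP 9.2.1 opens the randomized-treatment window at the first 177Lu-PSMA-617 dose, or at Cycle 1 Day 1 on control, and sets its end as follows: "up to 30 days after the date of the last administration of randomized treatment or the day prior to the initiation of subsequent anticancer treatment". The earlier of the two dates applies. SAP section 5 takes the last administration as the later of the last 177Lu-PSMA-617 dose and the last BSC/BSoC administration, and for the latter it states: "Date of last administration of BSC/BSoC is the end of treatment decision date recorded on the End of Treatment". Protocol 7.2 matches this: AE monitoring "will continue up to and including 30 days after the last dose of" 177Lu-PSMA-617 or the BSC/BSoC end-of-treatment decision, whichever is later. Protocol 3.4.5 makes the end of treatment depend on outcome: "Patients may continue treatment until radiographic progressive disease, withdrawal of consent, the occurrence of unacceptable toxicity", or an investigator's judgement that the patient is not benefiting.

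Protocol 8.8.1 states an intention on exposure: "The relationship between dose intensity, duration of exposure, and frequency and severity of adverse events will be explored by data tabulation". It names no estimator.

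**The concern.** A crude percentage compares like with like only if both arms are observed for about the same time. Here the observation time is itself an outcome. Patients leave treatment at progression, on withdrawal or when they need care that the study does not allow, and the design expects control patients to progress sooner. Protocol 8.1 also reports high early dropout on control. For that reason the primary rPFS analysis was restricted to patients randomized on or after 5 March 2019. SAP 5.3.2 draws the safety set from the whole FAS, so treated patients from before that date stay in the AE tables.

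At stake is the reading of the main between-arm safety tables. For an AE that owes nothing to 177Lu-PSMA-617, longer observation alone can produce an apparent excess on that arm. For an AE that the drug does cause, the crude difference mixes the drug effect with extra time at risk.

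**Working it through.** **Check on the proxy.** The documents give no figure for the AE comparison and no treatment durations. I use the planned rPFS medians in Protocol 8.3 (6 and 4 months) as a stand-in for time on treatment, so I first checked that they fit the plan's own power statement. With 364 events, 2:1 allocation, one-sided alpha 0.004 and HR 4/6, the Schoenfeld formula gives √(364 × 2/9) × ln 1.5 − 2.652 = 3.647 − 2.652 = 0.995, that is 84.0% power (82.9% at HR 0.67). The stated figure is 84%.

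**Model (assumption).** Treatment time is exponential with median m, so θ = ln 2 / m. The TEAE window is treatment time plus w = 30/30.4375 = 0.986 month. The first-AE hazard λ is constant and equal in both arms.

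- Mean window: m/ln 2 + w = 9.6 months (m = 6) and 6.8 months (m = 4).
- Proportion with at least one AE: 1 − exp(−λw) × θ/(θ + λ).

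**Worked case, λ = 0.10 per month.** exp(−0.0986) = 0.906. For m = 6, θ = 0.1155 and the proportion is 1 − 0.906 × 0.536 = 51.4%. For m = 4, θ = 0.1733 and it is 1 − 0.906 × 0.634 = 42.5%. The false excess is 8.9 points.

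| λ per month | 177Lu arm | Control | Difference (points) | Ratio |
|---|---|---|---|---|
| 0.01 | 8.9% | 6.4% | 2.5 | 1.39 |
| 0.03 | 22.9% | 17.2% | 5.7 | 1.33 |
| 0.05 | 33.6% | 26.1% | 7.4 | 1.28 |
| 0.10 | 51.4% | 42.5% | 8.9 | 1.21 |
| 0.20 | 69.9% | 61.9% | 8.1 | 1.13 |
| 0.50 | 88.5% | 84.3% | 4.3 | 1.05 |

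With equal medians (6 and 6) the difference is 0. If early dropout cut the control median treatment time to 3 months (an assumption, since no dropout rate is given), λ = 0.10 would give 51.4% against 36.8%, or 14.7 points.

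**AEs that cluster early.** Keep the same windows, with a hazard in both arms of 0.20 per month for 2 months and 0.02 afterwards. The crude proportions are 40.9% and 37.6%, a false excess of 3.4 points.

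**Behaviour of the candidate remedies.**

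- *Rate per 100 patient-years.* Under a constant hazard it recovers equality: a simulation at λ = 0.10 gave 119.9 and 120.0. In the early-clustering example it gives 82 on 177Lu-PSMA-617 against 100 on control, because the longer window adds low-risk time to the denominator. It then errs in the other direction.
- *Cumulative incidence at a fixed time.* It depends on the hazard up to that time and not on how long the window later stays open. Leaving deaths aside, at 6 months both arms would show 1 − exp(−0.60) = 45.1% in the constant-hazard case and 1 − exp(−(0.40 + 0.08)) = 38.1% in the early-clustering case.

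**The case against.** The strongest reply is that the plan already shows more than the crude tables, and that the error runs against the experimental drug.

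- SAP 9.2.6 tabulates AEs in long-term follow-up, so a reader who infers that AE collection stops after 30 days would be wrong. What stops is full-detail collection: follow-up AEs carry only term and grade, in a separate table.
- SAP 9.2.5 gives deaths within 6 and 12 weeks of randomization. These windows do not depend on the end of treatment, but they cover deaths only.
- SAP 9.2.4 tabulates TEAEs by cycle of onset, but states no at-risk denominator.
- SAP 5.4 and 5.4.1 plan AE summaries by number of 177Lu cycles received. A reader might conclude that the SAP dropped the Protocol 8.8.1 intention altogether. It survives here, but only within the 177Lu arm, so it cannot adjust a between-arm comparison.
- SAP 9.1 reports exposure by arm, which makes unequal observation visible without correcting for it.

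Several limits on size also stand. Planned rPFS is only a proxy. A constant hazard overstates the problem for early AEs. The full 30 days is added for everyone, although new anticancer therapy can close the window sooner. Patients who left before Cycle 1 Day 1 are outside the treated safety set, and about 557 of 814 patients were expected to be randomized after the remedial measures. The AE comparison is descriptive, with no test planned, and overstating toxicity is conservative for safety. None of this supplies a time-adjusted comparison between arms.

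**Conclusion.** The point holds as a moderate weakness. The between-arm TEAE comparison takes no account of time at risk, and the documents point to longer observation on 177Lu-PSMA-617. Under the assumed exponential treatment times, equal hazards give a false crude excess of about 2 to 9 points for constant rates of 0.01 to 0.5 per month (largest, 8.9 points, near 0.10) and about 3 points in the early-clustering example. The direction rests on treatment lasting longer on 177Lu-PSMA-617. That is probable from the planned medians and the reported control dropout, but no observed durations are given.

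A reader might go further and infer that any toxicity excess on 177Lu-PSMA-617 is an artefact, or that benefit and risk cannot be judged from this trial. The documents do not support that. The calculation concerns AEs with equal hazards in both arms, not toxicity specific to the drug, and the other planned outputs give partial information. What follows is narrower: the crude percentages alone do not separate toxicity from length of observation.

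**What to change.** In SAP 9.2.4, beside the crude tables, add by arm the cumulative incidence of the first event over time from treatment start, for any, serious, grade 3/4/5 and fatal TEAEs and for the safety topics of interest in SAP 9.2.7. Censor at the end of the TEAE window, treat death without the event as a competing event, and give 95% CIs at fixed times, for example 3, 6 and 12 months.

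Exposure-adjusted rates per 100 patient-years may be added as a supplement, with the caveat that for early-clustering AEs they can falsely favour the arm observed longer. State that between-arm safety conclusions use the time-adjusted summaries together with the crude percentages.

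The cost is SAP wording and a few more tables from dates already collected. The statistical price is the assumption that censoring at the end of the window is non-informative. That is open to question when patients stop for progression or lack of benefit, which is a reason to keep the crude tables alongside.
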